### **Background & Significance**

Enhanced recovery after surgery (**ERAS**) pathways play a critical role in the delivery of high-quality surgical care. These protocols incorporate multiple perioperative patient interventions including preemptive analgesia, measures to reduce postoperative nausea and emesis, fluid balance aimed at euvolemia, and both early ambulation and oral intake. ERAS pathways are significant because they have been shown to shorten recovery, decrease hospital stay, reduce complications/nosocomial infections, and conserve resources. Same-day discharge (**SDD**) is a central aspect of enhanced recovery pathways.

**SDD and ERAS protocols are part of a new initiative within the Women's Health Institute**, and their application for gynecologic surgery is of increasing interest across the country. To date, the focus of studies has largely been on laparoscopic and robotic hysterectomy in the benign and gynecologic oncology literature. Studies have consistently demonstrated both feasibility and safety of SDD after laparoscopic and robotic hysterectomy, with no significant increase in complications or readmissions as compared to discharge on postoperative day (**POD**) 1. In fact, a recent systematic review by Korsholm et al of 15 observational studies with nearly 12,000 patients revealed SDD is feasible, at a rate of nearly 80%, when patients are properly selected and careful surgical planning is performed. Studies have also demonstrated high patient satisfaction and less cost with SDD after minimally invasive hysterectomy. SDD has been applied in other minimally invasive gynecologic procedures, such as minimally invasive myomectomy, with low readmission rates (0.6% within 48 hours, 1.4% over 3 months).

ERAS pathways can have an important role in other areas of gynecologic surgery. In the field of urogynecology, quality of life reconstructive surgery is often performed to address symptoms of pelvic organ prolapse, urinary incontinence, and/or fecal incontinence. A prospective study by Kalogera et al evaluated the impact of an ERAS pathway for patients undergoing vaginal reconstructive surgeries for pelvic organ prolapse versus historical controls. In this cohort, patient satisfaction with perioperative care was high, mean duration of hospital stay was significantly reduced, and there were no differences in 30 day outcomes. In a case series by Zakaria and Levy, an ERAS pathway was utilized after vaginal hysterectomy, which permitted SDD in 96% of patients. Notably, only 5 of the 1071 patients required readmission or emergency room evaluation within 30 days of surgery. Taken together, these studies provide support for the application of ERAS pathways in urogynecology, where well-selected surgical candidates are undergoing surgeries appropriate for SDD.

Yet, to date, **only one research study has investigated the role of SDD after minimally invasive sacrocolpopexy**. A sacrocolpopexy is a surgery for pelvic organ prolapse in which a bridging piece of mesh is utilized to suspend the vaginal cuff to the anterior longitudinal ligament overlying the sacral promontory. This is an extensively studied and highly effective surgical technique to correct pelvic organ prolapse and is a mainstay in the field of urogynecology. A study by Faucheron et al evaluated SDD for robotic and laparoscopic ventral rectopexy, a similar mesh-augmented procedure that is performed for rectal prolapse, and concluded that SDD is feasible and safe. A preliminary study by Lloyd et al performed at the Cleveland Clinic within the Female Urology division investigated SDD after minimally invasive sacrocolpopexy (*article in press*). In this study, SDD was achieved in 10 of 12 patients (83.3%). The two patients who did not have SDD were due to case completion after 6PM, a preset case completion requirement. Outcomes were also retrospectively compared between patients who underwent SDD (N= 10) and patients who stayed overnight (N=30). Only one

patient had an emergency department visit on POD 20, due to an unrelated mechanical fall. Importantly, there were no major complications in either group requiring procedural interventions, new prescriptions, or additional interventions. Recently, a study by Kisby et al was published examining SDD after robotic-assisted sacrocolpopexy. In this retrospective study, 80 women underwent SDD compared to 192 who were discharged on  $\geq$ POD 1. This study found no difference in unplanned provider visits, emergency department visits or readmissions between the groups.

**We hypothesize that an ERAS protocol utilizing SDD for minimally invasive sacrocolpopexy is as safe as those that utilize discharge on POD 1 while incurring less total procedure-related costs and being acceptable as a post-op management plan for patients.** The *objective of this study* is to provide data which are necessary to widely implement SDD after a minimally invasive sacrocolpopexy. The results of this research *will have a significant impact* on increasing patient satisfaction, minimizing resource utilization, and improving clinical practice patterns in the field of urogynecology, both for this procedure and potentially other surgeries within our subspecialty.

### **Specific Aims**

**Aim 1.** To compare the incidence of adverse events in patients following a SDD protocol for minimally invasive sacrocolpopexy compared to those patients discharged on POD 1.

We hypothesize that there is no difference in the incidence of adverse events between SDD compared to discharge on POD 1 after minimally invasive sacrocolpopexy. Using the *Epic* electronic medical record (**EMR**), we will evaluate 1) the number of unscheduled office visits, patient-initiated calls for a surgery-related complication, emergency department visits, and readmissions/reoperations of patients who had a SDD protocol and 2) the severity of any adverse events using the Clavien Dindo Scale. We will utilize patient phone calls to inquire about any of the aforementioned events outside of our institution. We will compare incidence of postoperative adverse events between patients undergoing SDD versus a historical control group who were discharged on POD 1.

**Aim 2.** To compare the total procedure-related costs associated with SDD compared to discharge on POD 1 for minimally invasive sacrocolpopexy.

We hypothesize that the total costs associated with SDD following minimally invasive sacrocolpopexy is less than the same procedure with discharge on POD 1. We will utilize data from the billing function of *Epic* EMR to compare total procedure-related costs for each approach to minimally invasive sacrocolpopexy.

**Aim 3.** To determine patient satisfaction with SDD after minimally invasive sacrocolpopexy.

We hypothesize that patients will be satisfied with SDD after minimally invasive sacrocolpopexy. We plan to address this aim using a series of validated measures.

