### **Research Plan**

#### **1. Study Design**

This is a prospective cohort study evaluating safety, cost and patient satisfaction with SDD for patients undergoing minimally invasive sacrocolpopexy for pelvic organ prolapse. A prospectively collected, historical control group who underwent the same surgical procedure will be utilized to compare these outcomes when applicable. SDD will be facilitated in part by a utilizing novel patient education video created for this study and implementing an ERAS pathway. All patients meeting eligibility criteria will be approached for study participation. Outcomes will be assessed on POD 0/1 and at the routine post-operative follow up visit, generally at 6 weeks after surgery.

**Primary outcomes:** The primary outcome of this study is serious adverse events.

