### **3. Data Collection**

The EMR will be reviewed to collect preoperative, intraoperative, and POD 0 data points. We will use the following method to identify the occurrence of a procedure-related adverse event: The EMR will be reviewed for patient phone calls for a procedure-related complication, unscheduled office visits, emergency department visits, hospital readmissions or reoperations within 30 days, and adverse events occurring up to 6 weeks post-operatively. The adverse events of interest will include the following:

- Wound infection
- Hematoma
- Transfusion
- Pelvic abscess
- Osteomyelitis
- Venous thromboembolism (deep vein thrombosis or pulmonary embolism)
- Delayed bowel or urinary tract injury
- Bowel obstruction or ileus
- Cardiac or pulmonary complication
- Neurologic injury

We will also employ an approach that will allow us to capture events that may have been handled outside of the CCHS or in institutions that do not utilize *Epic*. To capture these data points if they exist, we will contact participants by telephone on POD 1 (within 24 hours of surgical completion time) to determine if they received any care from a facility outside of the CCHS and then again at the post-operative follow up visit, which generally occurs at 6 weeks. We will then use these data with the Clavien Dindo Scale to determine the severity of the adverse event, with a grade 3 or higher considered to be a serious adverse event, and we will compare this proportion to the reference proportion of 26.3%. A proportion of patients with grade 3 or higher less than 45.1% will be considered non-inferior to the reference.

As part of the effort to characterize the patient population, we will extract data regarding total procedure-related costs using the EMR. We will assess satisfaction using the quality of recovery questionnaire, visual analog scores for postoperative pain, and a patient satisfaction survey described by Fountain et al at the postoperative visit, which uses a Press Ganey scale for responses (See Appendix A). Please see data collection sheet for a comprehensive list of planned data points.

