### **4. Statistical Plan**

*Statistical analysis:* Categorical variables will be presented as n/N (%) with 95% confidence intervals. Continuous variables will be presented as mean +/-SD or median [range]. A Pearson's chi-square test or Fisher exact test will be used for frequencies and proportions of categorical values and t test or the non-parametric Wilcoxon rank sum test for mean values of continuously measured variables. P values  $\leq 0.05$  will be considered statistically significant and we will use SAS (version 9.4, The SAS Institute, Cary NC) as our statistical package to perform these analyses. The primary investigator will perform the statistical analysis with assistance from the WHI statistician.

We will use data from a historical control group discharged on POD 1 after minimally invasive sacrocolpopexy to examine Aim 1 and Aim 2. This is a cohort of 60 women matching our eligibility criteria from a prospective randomized trial of two different types of lightweight polypropylene mesh (IRB #14-354). This study completed recruitment 2017. It consists of a group of women who underwent minimally invasive sacrocolpopexy using the same surgical approaches, at the same institutions (main campus, Fairview and Hillcrest), and performed by the same surgeons as our study. The primary difference is that participants in that study and the cohort proposed here is that all participants were discharged home on POD 1. We will utilize this cohort to compare the incidence and severity of procedure-related adverse events and costs between SDD and POD 1. Comparisons on outcome measures will be done using either an ANOVA analysis or a student's t test for parametric continuous outcomes, a Kruskal-Wallis or Mann Whitney U test for non-parametric outcomes and a Chi-square test for all categorical outcomes. Logistic regression will be performed to control for confounding variables.

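### Aim 1 compares contact outcomes as one total per cohort, although controls were inpatients on the first night and could not generate a call, ED visit or readmission then

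*Combined protocol and SAP*

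**What the plan says.** Specific Aims, Aim 1, sets out the comparison: "We will compare incidence of postoperative adverse events between patients undergoing SDD versus a historical control group who were discharged on POD 1". The events it evaluates are unscheduled office visits, "patient-initiated calls for a surgery-related complication, emergency department visits, and readmissions/reoperations of patients who had a SDD protocol", together with Clavien Dindo severity. Calls, unscheduled visits and ED visits are also listed as secondary outcomes. Section 1 (Study Design) says that the historical controls will be used for these outcomes where applicable.

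Section 3 (Data Collection) sets the follow-up: "hospital readmissions or reoperations within 30 days, and adverse events occurring up to 6 weeks post-operatively". Whether the 30 days also governs calls and ED visits is not clear. Section 1 gives the assessment times: "Outcomes will be assessed on POD 0/1 and at the routine post-operative follow up visit, generally at 6 weeks after surgery".

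On the controls, section 4 (Statistical Plan) says "This is a cohort of 60 women matching our eligibility criteria" and that "all participants were discharged home on POD 1". It presents discharge timing as the main difference between the cohorts. The planned analyses are chi-square or Fisher tests, t or rank tests and logistic regression on overall outcomes. There is no analysis by period and no counterpart for first-night problems that were dealt with on the ward.

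**The concern.** A woman still in her index admission cannot produce a patient-initiated call, an ED visit or a readmission. For these outcomes the controls' first-night count is zero by construction. Pain or vomiting that a ward nurse handled in a control may appear as a call or ED visit in a woman who had gone home. Unscheduled office visits are affected less, since the one type named is a voiding trial and repeat trials fall 2 to 5 days after surgery.

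A total per cohort therefore mixes a period in which only SDD patients could have the outcome with a longer one in which both groups could. A difference in the total may be partly an artefact of where care was given. Similar totals would not tell a reader what happened on the first night. Logistic regression for confounders cannot repair an outcome that one cohort could not have for part of follow-up. The study is meant to support wider use of SDD, so the first night is the period readers will ask about.

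**Working it through.** **1. The plan's own figure, and whether this point touches it.** Inputs from section 4: n = 45, reference 26.3%, one-sided exact binomial test, power 80%. The 0.05 level is the plan's general one, as the sample-size paragraph gives none of its own.
- Smallest count with P(X ≥ c | 45, 0.263) ≤ 0.05: c = 18, exact level 0.031.
- Power at 45.1%: P(X ≥ 18 | 45, 0.451) = 0.798. Exactly 80% falls at 45.15%.
- Dropout: 45 / 0.97 = 46.4, rounded up to 47.

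The plan's 45.1% and 47 reproduce. The 60 controls do not enter this calculation, and inpatients can have grade 3 or higher events, so the primary decision carries no structural zero.

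**2. Size of the structural zero in a contact total.** Let q be the first-night contact rate in SDD patients and r the later rate, equal in both cohorts. Control total = r. SDD total = 1 − (1 − q)(1 − r). The documents give no contact rates, so q is assumed. For r, the plan's 12% and 26.3%, which are adverse-event rates, serve only as stand-ins.

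| q | SDD total, r = 12% | SDD total, r = 26.3% |
|---|---|---|
| 2% | 13.8% | 27.8% |
| 5% | 16.4% | 30.0% |
| 10% | 20.8% | 33.7% |

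The excess is 1.5 to 8.8 percentage points with no difference at all after the first night. It shrinks if some SDD patients stay overnight. With the pilot's 10 of 12 going home, q = 5% becomes 0.05 × 10/12 = 4.2%, and the total for r = 12% is 1 − 0.958 × 0.88 = 15.7%. Power of the pooled 45 versus 60 comparison to show these excesses is about 4% to 24% (normal approximation, two-sided 0.05). The artefact would mostly shift estimates rather than reach significance.

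**3. Why first-night contacts should not be tested against controls.** With controls fixed at 0/60, 3/45 in SDD gives Fisher p = 0.076 and 4/45 gives p = 0.031. Four telephone calls would look significant against a zero that could not have been anything else. The first night needs a clinical outcome that both cohorts can have.

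**4. What an early window can show.** Take the plan's 12% expected rate, assume 20% to 40% of events are early (2.4% to 4.8%), and let SDD double that early risk. Two-sided Fisher power, 45 versus 60:
- Early window: 4.8% v 2.4%, power 5%; 9.6% v 4.8%, power 12%.
- Total: 14.4% v 12%, power 4%; 16.8% v 12%, power 8%.

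The early window is nearly as weak as the total. Its value is description. With 0 of 45 SDD patients having an ED visit or readmission within 48 hours, the one-sided 95% upper limit is 1 − 0.05^(1/45) = 6.4%.

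**The case against.** The best defence is that Aim 1 concerns an SDD protocol as a whole. A total counted from surgery is then a legitimate policy comparison, and a first-night ED visit is a real consequence of sending a patient home. That stands, and it is why the total should be kept and why a comparison restricted to the period after POD 1 should not replace it.

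A second defence is that the plan never says in so many words that contact counts will be compared between cohorts. Aim 1 counts them in SDD patients, and section 3 treats them as the means of finding adverse events. This has some force. But Aim 1 places them under a comparison with controls, and section 1 allows that comparison. If they serve only to find events, first-night problems are still found by different routes in the two cohorts.

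A reader might infer that the contact totals are simply tilted against SDD. The documents do not support that. The post-operative follow-up section plans team-initiated calls on POD 0 and POD 1, which could absorb concerns that would otherwise be patient-initiated calls, and none are described for controls. Patients who do not meet discharge criteria are kept overnight.

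It is also true that early data are already gathered, at POD 0/1 and by a call within 24 hours. What is missing is their analysis.

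**Conclusion.** The point holds for the secondary contact outcomes of Aim 1: patient-initiated calls, ED visits, readmissions and, to a lesser extent, unscheduled visits. It does not hold for reoperations or for the primary decision. The structural zero follows from the documents alone. Its size does not: the 1.5 to 8.8 points above rest on assumed contact rates, equal later rates, and every SDD patient going home. The net direction cannot be settled from the plan.

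Two stronger readings are tempting. One is that the 6-week serious-event total is dominated by late events that hide first-night harm. The documents give no timing. Their event list includes hematoma, transfusion and cardiac or pulmonary complications, which can arise early, as well as wound infection and abscess. The POD 20 event in the pilot was an ED visit for an unrelated fall. The other reading is that a split would make early harm detectable. At 45 versus 60 it would not, as step 4 shows.

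The change is worth making because the comparison as planned can mislead and the correction is cheap. It does not alter the sample size or the primary criterion.

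**What to change.** - Keep the total from surgery as planned.
- Pre-specify a split of each Aim 1 outcome by onset date into (1) end of surgery to POD 1 and (2) after POD 1, with one boundary rule for both cohorts. The end of POD 1 would serve, since every control had been discharged by then.
- Show the between-cohort comparison of contacts both in total and for window 2.
- For window 1, compare clinical events by Clavien Dindo grade wherever managed. Use the inpatient chart for controls, and calls, ED visits, readmissions or the overnight stay for SDD patients. State how SDD patients kept overnight are counted.
- Report the SDD rate of ED visit or readmission within 48 hours with an exact confidence interval.
- State that the early window is descriptive, citing the 5% to 12% power above.
- State the follow-up window for calls and ED visits.

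The cost is protocol wording, event dates from the electronic record, first-night chart review for 60 controls and one more table. No new visits or patients are needed, and 45, 47 and 45.1% are unchanged.

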*Voiding Trial:* Our standard voiding protocol will be performed in the PACU when the patient is able to stand and ambulate to the restroom. The bladder will be retrograde filled with 300 ml of sterile fluid. The Foley catheter is then removed and the patient must void 200 ml (or 2/3 of the instilled volume if the patient is not able to tolerate the full amount). If the patient is unable to void then the Foley catheter will be replaced and she will be given Foley teaching or, alternatively, the patient may be taught intermittent self-catheterization. A repeat voiding trial will be scheduled within 2-5 days in the outpatient clinic.

*Post-operative Assessment and Disposition:* All patients will be assessed by the primary surgical team prior to discharge home. Post-operative requirements include: Ability to tolerate oral fluids and medications, adequate pain control and ability to walk with assistance. Patients not meeting criteria for discharge home at the conclusion of the recovery period will be kept for observation overnight as an extended recovery.

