### Exclusion Criteria:

- Laparoscopic, robotic, or open abdominal surgical procedures that require an overnight admission. This may be due to unanticipated additional intraoperative procedures or surgical complications such as unintentional cystotomy or enterotomy, hemorrhage, or anesthetic complication.
- Patients undergoing concomitant laparoscopic colorectal procedures or anal sphincteroplasty
- Surgery start time after 1:00PM, as previous studies have determined this is associated with a decreased likelihood of SDD
- Pregnancy or positive hCG testing, which is standard of care preoperative testing.

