**Appendix A**

**Minimally Invasive Sacrocolpopexy Survey**

The following questions are asking about your recent prolapse surgery.

Check the box that applies:

1. When did you go home from the hospital? (check one box)  
 The day of surgery                       2 or more days after surgery  
 1 day after surgery
  
2. How many weeks has it been since your surgery? (check one box)

- 4 weeks                       6 weeks  
 5 weeks                       more than 6 weeks

3. Please rate the education that you received in this clinic before surgery that prepared you for your surgery and recovery after surgery.

- Very poor                       Good  
 Poor                               Very good  
 Fair

4. Please rate the care that you received in this clinic before your surgery.

- Very poor                       Good  
 Poor                               Very good  
 Fair

5. Please rate the care that you received in the hospital after your surgery (before going home).

- Very poor                       Good  
 Poor                               Very good  
 Fair

6. Please rate your postoperative recovery after surgery through today.

- Very poor                       Good  
 Poor                               Very good  
 Fair

7. Overall how satisfied are you with your entire surgical experience at Cleveland Clinic for this most recent surgery?

- Very satisfied                       Somewhat dissatisfied  
 Somewhat satisfied                       Very dissatisfied  
 Neither satisfied or dissatisfied

8. Overall how satisfied are you with the pre-operative video education you received?

- Very satisfied                       Somewhat dissatisfied  
 Somewhat satisfied                       Very dissatisfied  
 Neither satisfied or dissatisfied

Please agree or disagree...

9. The pre-operative video education was helpful in preparing me for surgery and recovery after surgery.

- Strongly agree                       Disagree  
 Agree                                   Strongly disagree  
 Neither agree or disagree

10. I would recommend my friends/family to go home on the day of their surgery.

- Strongly agree                       Disagree  
 Agree                                   Strongly disagree  
 Neither agree or disagree

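### Aim 1 defines the same-day discharge (SDD) group inconsistently, and no rule says how women kept overnight under the SDD protocol are analysed; dropping them would overstate the policy's cost saving

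*Combined protocol and SAP*

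**What the plan says.** **SDD group defined by protocol.** In Specific Aims, the Aim 1 objective is "To compare the incidence of adverse events in patients following a SDD protocol for minimally invasive sacrocolpopexy", and the events to be counted include "readmissions/reoperations of patients who had a SDD protocol". Both describe planned management.

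**SDD group defined by discharge.** The same Aim 1 text then states the comparison: "We will compare incidence of postoperative adverse events between patients undergoing SDD versus a historical control group who were discharged on POD 1". Aim 2 is "To compare the total procedure-related costs associated with SDD compared to discharge on POD 1". Section 4 (Statistical Plan) likewise sets SDD against POD 1. Neither says whether planned or actual discharge is meant.

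**Women kept overnight.** Day of Surgery says: "Patients not meeting criteria for discharge home at the conclusion of the recovery period will be kept for observation overnight as an extended recovery". The criteria concern oral intake, pain control and walking. The Appendix A survey offers "1 day after surgery" and a longer stay as answers to its first question, so such women appear to remain in follow-up.

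**Controls.** Section 4 describes 60 women from an earlier mesh trial who match the eligibility criteria, and says of them that "all participants were discharged home on POD 1".

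**Not stated.** No section defines an analysis set by planned or actual discharge. The proportion discharged the same day is not among the primary or secondary outcomes.

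**The concern.** A woman who is managed under the SDD protocol, misses the recovery criteria and stays the night receives much the same overnight stay as the controls. Whether she counts as SDD is left open, and the wording of the operative comparison points towards leaving her out. The Background supports that reading. In describing the same-institution pilot it uses the expression for having undergone SDD only for the 10 of 12 women who actually went home that day.

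The Background states the purpose as providing data needed to implement SDD widely, as a management plan. That is a question about a policy, and the policy includes its failures. Failing on pain, intake or walking is an early result of the policy, so a comparison restricted to successes conditions on something that happens after surgery. It would contrast successful SDD with a planned night in hospital. The cost aim is the most exposed, because the extra night is a direct cost of the policy.

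**Working it through.** **1. Reproduce the plan's own figure.** Inputs from section 4: reference 26.3%, n = 45, one-sided exact binomial test, power 80%. Alpha of 0.05 is the general significance level and is not restated for the sample size.
- The smallest r with P(X ≥ r | 45, 0.263) ≤ 0.05 is r = 18 (actual alpha 0.031).
- Solving P(X ≥ 18 | 45, p) = 0.80 gives p = 45.15%. Power at 45.1% is 79.8%.
- Dropout: 45/0.97 = 46.4, rounded up to 47.

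The stated 45.1% and 47 are reproduced. They assume all 45 evaluable women are analysed.

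**2. How many women are affected.** The Background cites three same-day rates: 96% (vaginal hysterectomy series), 83.3% (10/12, same-institution sacrocolpopexy pilot) and nearly 80% (review of minimally invasive hysterectomy). Overnight women = 45 × (1 − s).

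| Same-day rate s | Overnight, of 45 | Remaining |
|---|---|---|
| 96% | 1.8 | 43.2 |
| 83.3% | 7.5 | 37.5 |
| 80% | 9.0 | 36.0 |

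**3. Cost (Aim 2).** Let S be the mean saving, against a POD 1 control, for a woman who goes home the same day. Assume an overnight SDD woman saves nothing. The policy's saving per woman is s × S, while an analysis of same-day women only reports S. The overstatement is 1/s − 1:
- s = 0.96: 1/0.96 − 1 = 4%
- s = 0.833: 1/0.833 − 1 = 20%
- s = 0.80: 1/0.80 − 1 = 25%

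If an overnight SDD woman costs less than a control, the figures shrink; if she costs more, they grow.

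**4. Events (Aim 1).** Let RR be the event risk of overnight women relative to same-day women. The documents give no value, so 1 to 3 is an assumed range. Rate in same-day women = overall rate / (s + (1 − s) × RR).

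| Overall rate | s | RR 1 | RR 2 | RR 3 |
|---|---|---|---|---|
| 12% | 96% | 12.0% | 11.5% | 11.1% |
| 12% | 83.3% | 12.0% | 10.3% | 9.0% |
| 12% | 80% | 12.0% | 10.0% | 8.6% |
| 26.3% | 96% | 26.3% | 25.3% | 24.3% |
| 26.3% | 83.3% | 26.3% | 22.5% | 19.7% |
| 26.3% | 80% | 26.3% | 21.9% | 18.8% |

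The shift is 0 to about 3 points at the plan's expected 12%, and 0 to about 7.5 points at 26.3%.

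**5. Primary endpoint.** It is compared with a fixed 26.3% and a limit of 45.1%, not with the 60 controls. Every rate in step 4 is far below 45.1%. The number analysed does matter for the stated power. Repeating step 1 at alpha 0.05:

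| n | r | Detectable at 80% power | Power at 45.1% |
|---|---|---|---|
| 45 | 18 | 45.1% | 79.8% |
| 43 | 17 | 44.8% | 81.2% |
| 38 | 16 | 47.6% | 70.2% |
| 37 | 15 | 46.1% | 76.4% |
| 36 | 15 | 47.3% | 71.8% |

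The uneven pattern comes from the discreteness of the exact test. Losing about 2 women makes no practical difference; losing 7 to 9 costs about 3 to 10 points of power.

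**The case against.** The strongest reply is that this is loose wording and not a planned as-discharged analysis. Aim 1 uses protocol-based wording twice, the Background hypothesis concerns a protocol that uses SDD, and the comparison sentence may be shorthand. Day of Surgery withdraws nobody, and the survey expects answers from women who stayed. If they are retained, this bias does not arise, and the cost outcome already covers post-operative hospitalization. All of that stands. It shows that the documents permit the sound analysis, but not that they commit to it.

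The rates are also open to challenge. They come from other studies, two of them of different operations. Both pilot failures were due to late case completion, and this protocol excludes starts after 1:00 PM. That stands too, and it is why 96% belongs in the range.

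Three stronger readings are tempting, and the documents do not support them.
- A reader might infer that both cohorts are defined by actual discharge day. For the SDD cohort, the protocol-based wording contradicts this.
- A reader might infer that SDD is flattered on adverse events. That requires overnight women to have more events. This is plausible but not shown, and the pilot's two failures were not complications.
- A reader might infer that the controls were filtered on discharge day. The statement about their discharge can equally be a description of what happened. If long-stay controls had been left out, the bias would run against SDD, and no section shows that any existed.

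Finally, one might say the exclusion of "Laparoscopic, robotic, or open abdominal surgical procedures that require an overnight admission" already settles the matter. Its examples are additional procedures and complications of the operation. It does not reach a woman whose operation was uneventful but who misses the recovery criteria.

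**Conclusion.** The concern holds as an inconsistency in the definition of the SDD group together with a missing analysis-set rule. The documents do not commit to an as-discharged analysis, but the operative comparison, read literally, is one.

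If overnight women are left out, the cost saving attributed to the SDD policy is overstated by about 4% to 25%. That range assumes an overnight SDD woman costs about the same as a POD 1 control, and that same-day rates of 96% to 80% from other studies apply here. The effect on event rates runs from none to a few points at the expected 12%, and its direction is not established. The primary verdict would hardly change. The impact falls mainly on Aim 2 and on the Aim 1 comparison with the 60 controls. It is worth correcting before analysis, because the choice of group should not be made after the discharge days and costs are known.

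**What to change.** - In Aims 1 and 2 and section 4, make the main analysis all enrolled women managed under the SDD protocol, whatever their actual discharge day. Use one phrase for this group throughout.
- Charge the extended-recovery night to the SDD cohort.
- Report women actually discharged the same day only as a sensitivity analysis.
- Add the proportion discharged the same day, with its 95% CI, to the secondary outcomes.
- Select the historical controls by eligibility and planned POD 1 discharge, and state whether any stayed longer. If some did, keep them.

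The cost is a change of wording: length of stay and billing data should already be in the EMR for the SDD cohort, and the stated sample size is unaffected. The price to the sponsor is a smaller estimated cost saving wherever women stay overnight.
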